#### 11.2.10 Discharge from hospital data

The dataset is an extraction from the HO domain (Reported terms equal to 'HOSPITALIZATION AT RANDOMIZATION'), merged to its supplemental domain, in a basic data structure.

The following parameters/ analysis value are defined:

**Actual time from first study treatment intake to discharge (hours)** is calculated as follows: (date/ time of first study treatment intake - date/ time of discharge)/ 3600.

**Time from first study treatment intake to discharge** is defined as follows:

- Equal to '6 hours' when the answer to 'Was the subject discharge at 6h after study drug intake?' is equal to 'Yes',

- Equal to 'from 6 through 12 hours' when the answer to 'Was the subject discharge up to 12h after study drug intake?' is equal to 'Yes',
- Equal to 'after 12 hours' when the answer to 'Was the subject discharge up to 12h after study drug intake?' is equal to 'No'.

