### **Appendix 3 Adverse events of special interest**

AESIs will include the anticipated risks of treatment with ACT-334441 or the known class effects or the events that may be related to SLE comorbidities (e.g., cardiovascular AEs) and will address the following safety areas:

- Effect on HR and rhythm related AEs
- Hypotension related AEs
- Hypertension related AEs
- Hepatobiliary disorders / liver enzyme abnormality related AEs
- Pulmonary related AEs
- Eye disorders related AEs
- Infection related AEs
- Skin malignancy related AEs
- Malignancy (non-skin) related AEs
- Cardiovascular related AEs

A list of AESIs (MedDRA preferred terms) will be defined in the SAP.

---

**Appendix 4      Criteria for discharge from hospital on Day 1 and on the first day  
of re-initiation following treatment interruptions**

At the time of discharge (i.e., 6 h post-dose) on Day 1 and on the first day of re-initiation of study treatment following drug interruptions, the following criteria must be met:

- ECG-derived resting HR > 45 bpm; and if HR < 50 bpm it must not be the lowest value post-dose
- SBP > 90 mmHg;
- QTcF < 500 ms;
- No persistent ECG abnormality (e.g., AV block second degree or higher) or ongoing AE requiring continued hospitalization.

Should the subject not meet the criteria for discharge 6 h post-dose, she/he will be monitored until 12 h post-dose with 12-lead ECG and BP measurements performed hourly and may be discharged after any of the hourly measurements, provided that discharge criteria are met until 12 h post-dose. If at 12 h post-dose, the subject does not meet discharge criteria, he/she must be permanently discontinued from study treatment. Subjects who are permanently discontinued should not be discharged from the monitored setting before vital signs return to near baseline values and until there are no persistent ECG abnormalities (e.g., AV block second degree or higher) or ongoing AE requiring continued hospitalization, or until a diagnosis is established.

**Appendix 5 American College of Cardiology / American Heart Association /  
American College of Physicians Training Requirements for  
Performance and Interpretation of Adult Transthoracic  
Echocardiography**

	Cumulative Duration of Training	Minimum Total Number of Examinations Performed	Minimum Number of Examinations Interpreted
Level 1	3 months	75	150
Level 2	6 months	150 (75 additional)	300 (150 additional)

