### 5.8.9 Discharge from hospital at day 1/re-initiation

The subject's eligibility for discharge or study drug discontinuation at Visit 2 (Randomization/ Day 1) or study treatment re-initiation is independently assessed by the cardiac safety assessor and collected in the 'Discharge from Hospital at Day 1/Re-Initiation'. The variables of interest are:

- Actual time from first study treatment intake to discharge (hours);
- Time from first study treatment intake to discharge, derived from the actual time computed above (at 6 hours, after 6 through 12 hours, after 12 hours);
- Reason for non-discharge at 6 hours, as collected in the eCRF;
- Reason for non-discharge from 6 to 12 hours, as collected in the eCRF;

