### 11.2.9 Medical history data, SLE specific

This dataset contains information from Medical History (MH) Domain (restricted to category equal to SYSTEMIC LUPUS ERYTHEMATOSUS RELEVANT DISEASE HISTORY) and its supplemental domain, in a basic data structure.

Each criterion is mapped into a parameter. The analysis value is equal to the occurrence of the pre-specified event.

In addition, the following parameters are derived:

- **Time from first SLE symptoms (years) to informed consent signature** is calculated as follows: (Informed consent date - date of first symptoms)/365.25.

- **Time from SLE diagnosis (years) to informed consent signature** is calculated as follows: (Informed consent date - date of SLE diagnosis)/365.25.
- **Number of SLE symptoms** according to ACR criteria [ACR 1997] **met in the past** is calculated for each subject as the number of observations with Event Pre-Specified equal to Y and Occurrence equal to Y and End Relative to Reference Time Point equal to BEFORE.
- **Number of SLE symptoms** according to ACR criteria [ACR 1997] **started more than 6 months prior to screening** is calculated for each subject as the number of observations with Event Pre-Specified equal to Y and Occurrence equal to Y and Did it start more than 6 months prior? equal to Y.
- **Number of SLE symptoms** according to ACR criteria [ACR 1997] **ongoing at screening** is calculated for each subject as the number of observations with Event Pre-Specified equal to Y and Occurrence equal to Y and End Relative to Reference Time Point equal to ONGOING.
- **Number of SLE symptoms** according to ACR criteria [ACR 1997] **met either serially or simultaneously** is calculated for each subject as the number of observations with Event Pre-Specified equal to Y and Occurrence equal to Y.

For each **Number of SLE symptoms** computed, the analysis value is further categorized in 0-3 and 4-11.

- **Presence of a documented historical positive ANA** is equal to Y when there is at least one observation in LB Domain with Group ID equal to 'PREVIOUS TESTINGS' and Lab Test or Examination Short Name equal to 'ANA'.
- **Presence of a documented historical positive anti-dsDNA** is equal to Y when there is least one observation in LB Domain with Group ID equal to 'PREVIOUS TESTINGS' and Lab Test or Examination Short Name equal to 'ADSDNA'.

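### SAP 11.2.10 computes time to hospital discharge with the operands reversed, so every value is negative, and SAP 5.8.9 and 11.2.10 take the discharge categories from different sources

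*SAP*

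**What the plan says.** SAP 5.8.9 lists the discharge variables. The first is "Actual time from first study treatment intake to discharge (hours". The second is the same time in categories, and its source is stated: "derived from the actual time computed above (at 6 hours, after 6 through 12 hours, after 12 hours".

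SAP 11.2.10 gives the derivations. The continuous time is "date/ time of first study treatment intake - date/ time of discharge)/ 3600". The categories are then defined without using that time. The first is "Equal to '6 hours' when the answer to 'Was the subject discharge at 6h after study drug intake?' is equal to 'Yes" and the last is "Equal to 'after 12 hours' when the answer to 'Was the subject discharge up to 12h after study drug intake?' is equal to 'No". The middle category likewise rests on a Yes answer to the question about discharge up to 12 h.

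Protocol Appendix 4 fixes the order of events. Its discharge criteria apply "At the time of discharge (i.e., 6 h post-dose) on Day 1 and on the first day of re-initiation of study treatment following drug interruptions", and a subject who does not meet them is monitored until 12 h post-dose.

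**The concern.** There are two separate problems in one variable.

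The first is the sign. The variable is named as time from intake to discharge, but the formula subtracts the later event from the earlier one.

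The second is that two sections of the SAP give different sources for the same categories. If a programmer follows 5.8.9, the faulty sign passes into the categories. If the programmer follows 11.2.10, it does not. At stake is whether the listed or displayed discharge time, and the share of subjects discharged later than 6 h in each dose group, depends on which section was programmed.

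**Working it through.** The SAP states no numerical result for this variable, so there is no figure to reproduce. The check evaluates the formula and compares the two category rules.

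**Inputs.** The formula and the eCRF rule come from SAP 11.2.10, and the category bounds from SAP 5.8.9. The order of events (discharge after dose) comes from Protocol Appendix 4. The clock times below are illustrative.

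**Step 1: sign.** Take a dose at 09:00 and discharge at 15:10.

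- As written: (09:00 - 15:10) = -22,200 s; -22,200 / 3600 = -6.17 h.
- Operands swapped: (15:10 - 09:00) = 22,200 s; 22,200 / 3600 = +6.17 h.

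The divisor is right for a difference in seconds, so only the sign is wrong.

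**Step 2: is there a sign convention that explains it?** No. SAP 11.2.9 computes disease duration as "Informed consent date - date of first symptoms)/365.25", later minus earlier. SAP 5.2.2.1 does the same, and SAP 11.2.5.1 computes treatment duration as the latest end date minus the earliest start date, plus 1. SAP 11.2.10 is out of step with all three.

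**Step 3: categories under 5.8.9.** The bounds are applied to the computed time for assumed discharges 6 to 24 h after the dose. The category at 6 hours is read as 6 or less, with no tolerance; this is an assumption, because the SAP gives no tolerance.

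| Discharge after dose (h) | Value as written (h) | Category as written | Value with operands swapped (h) | Category with operands swapped |
|---|---|---|---|---|
| 6 | -6 | at 6 | 6 | at 6 |
| 6.5 | -6.5 | at 6 | 6.5 | after 6 through 12 |
| 9 | -9 | at 6 | 9 | after 6 through 12 |
| 12 | -12 | at 6 | 12 | after 6 through 12 |
| 13 | -13 | at 6 | 13 | after 12 |
| 24 | -24 | at 6 | 24 | after 12 |

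As written, the two later categories are always empty.

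**Step 4: categories under 11.2.10.** The site's answers decide, so the sign is irrelevant.

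**Step 5: do the two sources agree once the sign is corrected?** Not necessarily. Suppose a subject leaves at 6.5 h and the site answers Yes to discharge at 6 h. Under 11.2.10 this subject is in the 6 hours category; under 5.8.9 with a strict cut, in the category after 6 through 12 hours. Swapping the operands therefore does not by itself settle which source applies.

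**The case against.** The strongest reply is that the SAP already shows which section governs. The opening of SAP 5.8 refers the reader to Section 11 for details of how safety variables are computed, and Section 11 sets out the eCRF rule category by category. Read that way, the reversed sign never reaches the categories, and what remains is loose wording in 5.8.9. This largely stands. It does not repair the continuous variable, and it leaves 5.8.9 stating a source that 11.2.10 does not use.

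The reach is also limited. SAP 10.9 sets out the safety analyses and names no summary of time to discharge; it commits only to listing all safety data. SAP 13 shows no list of outputs in the available text, so a table may exist but cannot be assumed. A column of negative hours would also probably be noticed. All of this stands and keeps the point minor.

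A reader might infer three stronger things that the documents do not support:

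- **That the trial would report no delayed discharges.** This requires 5.8.9 to be programmed on the negative values and the eCRF rule to be ignored.
- **That, with the sign corrected, nearly every subject would count as delayed because release follows the 6 h ECG and blood pressure check.** This needs a strict 6.00 h cut and actual release times. The documents give neither, and Appendix 4 itself equates discharge with 6 h post-dose.
- **That re-initiation discharges are lost because 11.2.10 extracts only the hospitalization at randomization.** Both time variables in 5.8.9 run from first study treatment intake, which fits that extraction. The documents do not show how re-initiation stays are coded in the source data.

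**Conclusion.** Wrong as written, minor. Two things are certain from the text: the continuous time in SAP 11.2.10 has the wrong sign for every subject, with the correct magnitude, and SAP 5.8.9 and 11.2.10 name different sources for the categories.

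Any misclassification is conditional. It arises if 5.8.9 is programmed on the signed value, or, after the sign is corrected, for releases shortly after 6 h under a strict cut. How many subjects that would involve cannot be stated from the documents.

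The effect stops at a descriptive first-dose safety variable and whatever listing or display is built from it. The change in lymphocyte count and its dose-response test are untouched. Eligibility for discharge is judged on site by the cardiac safety assessor (Protocol 3.3.3 and Appendix 4). Failure to meet the criteria counts towards the stopping rules directly (Protocol 9.3, Table 4), without the derived hours.

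**What to change.** 1. In SAP 11.2.10, compute the time as (date/time of discharge - date/time of first study treatment intake)/3600.
2. In SAP 5.8.9, remove the statement that the categories come from the computed time, and refer instead to the eCRF-answer rule of 11.2.10, so that one source is named.

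Both are changes of SAP wording, with the matching line of programming. No new data are needed, and no clinical rule changes.

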### 11.2.11 12-lead ECG, parameters data

This dataset contains data extracted from the Electrocardiogram Results (EG) Domain, restricted to the observations with Category equal to ('MEASUREMENT' or 'INTERPRETATION') and Method equal to '12 LEAD STANDARD' in a basic data structure.

The following analysis parameters are defined:

| ADaM variables |                |   | SDTM variables  |  |                |
|----------------|----------------|---|-----------------|--|----------------|
| Parameter (N)  | Parameter Code | Parameter                                   | Test Short Name | Test Name                              | Standard Units |
| 2              | EGHRMN         | Heart rate (bpm)                            | EGHRMN          | ECG Mean Heart Rate                    | beats/min      |
| 3              | PRMEAN         | PR Duration (msec)                          | PRMEAN          | Summary (Mean) PR Duration             | msec           |
| 4              | QRSDUR         | QRS Duration (msec)                         | QRSDUR          | Summary (Mean) QRS Duration            | msec           |
| 6              | QTCB           | QTcB-Bazett's Correction Formula (msec)     | QTCB            | QTcB - Bazett's Correction Formula     | msec           |
| 7              | QTCF           | QTcF-Fridericia's Correction Formula (msec) | QTCF            | QTcF - Fridericia's Correction Formula | msec           |
| 5              | QTMEAN         | QT Duration (msec)                          | QTMEAN          | Summary (Mean) QT Duration             | msec           |
| 1*             | RRMEAN         | RR Duration (msec)                          | RRMEAN          | Summary (Mean) RR Duration             | msec           |
| 8              | INTP           | Interpretation                              | INTP            | Interpretation                         |                |

\*Included in the listings but excluded from summary tables

For these analysis parameters (1 to 7), **Baseline, Absolute value at each post-baseline assessment and Absolute change from baseline to each post-baseline assessment** variables are populated as described in the general section.

The occurrence of abnormalities, as defined in table 'treatment emergent notable abnormalities', is populated for each post-baseline assessment individually. In addition, the occurrence of at least one 'Low' and at least one 'High' treatment-emergent

abnormality is derived on the subject level at the following time points: from 1 hour post-dose on Day 1 up to discharge, from discharge on Day 1 through EOT and at any time post-baseline.

There is also a parameter defined corresponding to the interpretation of the cardiologist. Additional comments he may have are extracted from the Comments (CO) Domain.

#### **11.2.12 12-lead ECG, findings data**

The dataset contains the observations extracted from the EG Domain with Category equals to 'FINDING' and Method equals to '12 LEAD STANDARD', in an occurrence data structure. Each finding is mapped now into an event.

Findings are considered '**Treatment Emergent**' if the date/time of the ECG is after the first study treatment intake.

#### **11.2.13 24 hour Holter-ECG, parameters data**

This dataset contains, in a basic data structure, only 2 tests extracted from EG Domain for Method equal to '12 LEAD HOLTER':

- 'ECG Mean Heart Rate', on observations with Category equal to 'MEASUREMENT' and Subcategory equal to 'DIARYP' (Diary Period)
- 'Holter Overall Interpretation'

For parameter equal to 'Mean Heart Rate (bpm)', the following variables are defined:

##### **Analysis Flag**

If several ECG (ECG reference ID) are available for 'V1 - Screening visit', only the most recent is taken into account (Group ID equal to "REPEAT").

##### **Analysis time point**

For Holters performed during screening period, the analysis time point for each hourly measurement is defined with respect to the study treatment intake on Day 1. Let's assume a Holter (screening) starting on 05-FEB-2017 at 11:03 and a first study treatment intake on 03-MAR-2017 at 10:53. On Day 1, the 1st hour starts at 10:53 and ends at 11:53. It is time-matched with the screening record starting at 11:03 and ending at 12:03.

For Holters performed on day 1, the analysis time point for each hourly measurement is defined with respect to the study drug intake. It is equal to 0 for records with a start time of the interval prior to time of study drug intake.

**Absolute change from baseline** (time-matched change from Visit 1 (Screening) to Visit 2 (Randomization/ Day 1) ) is defined as post-baseline value minus baseline value for each hourly time-matched measurement, i.e., a positive sign indicates an increase as compared to baseline.

For parameter equal to 'Holter Overall Interpretation', the analysis value is the opinion of the cardiologist recorded as 'NORMAL' or 'ABNORMAL'.

#### 11.2.14 24 hour Holter-ECG, findings data

This dataset regroups information from EG Domain (restricted to observations with Test equal to 'Holter Overall Interpretation') and the CO Domain. It contains any additional comments from the central reader mapped into a basic data structure.

For each Holter, the cardiologist provides his overall interpretation as 'NORMAL', 'ABNORMAL' and describes the potential findings in the comment section.

The findings to be extracted from the comment field(s) are the following:

**Table 13 Potential Holter-ECG Findings**

|    | Reported Term  | Preferred Term   |
|----|--|--|
| 1  | FREQUENT VPCS (IN HOURS)   | FREQUENT VPCS (IN HOURS)   |
| 2  | FREQUENT VPCS (GREATER THAN 30 VPCS IN ONE HOUR)                     | FREQUENT VPCS (GREATER THAN 30 VPCS IN ONE HOUR)                     |
| 3  | NONSUSTAINED VENTRICULAR TACHYCARDIA ( )                             | NONSUSTAINED VENTRICULAR TACHYCARDIA                                 |
| 4  | SUSTAINED VENTRICULAR TACHYCARDIA ( )                                | SUSTAINED VENTRICULAR TACHYCARDIA                                    |
| 5  | TORSADE DE POINTES   | TORSADE DE POINTES   |
| 6  | VENTRICULAR FIBRILLATION OR VENTRICULAR FLUTTER ( )                  | VENTRICULAR FIBRILLATION OR VENTRICULAR FLUTTER                      |
| 7  | FREQUENT SHORT EPISODES OF NONSUSTAINED SUPRAVENTRICULAR TACHYCARDIA | FREQUENT SHORT EPISODES OF NONSUSTAINED SUPRAVENTRICULAR TACHYCARDIA |
| 8  | ATRIAL FIBRILLATION ( )  | ATRIAL FIBRILLATION  |
| 9  | ATRIAL FLUTTER ( )   | ATRIAL FLUTTER   |
| 10 | MOBITZ I (WENCKEBACH) 2ND DEGREE AV BLOCK ( )                        | MOBITZ I (WENCKEBACH) 2ND DEGREE AV BLOCK                            |
| 11 | 2:1 AV BLOCK ( )   | 2:1 AV BLOCK   |
| 12 | HIGH GRADE AV BLOCK ( )  | HIGH GRADE AV BLOCK  |
| 13 | MOBITZ II 2ND DEGREE AV BLOCK ( )                                    | MOBITZ II 2ND DEGREE AV BLOCK  |
| 14 | COMPLETE HEART BLOCK ( )   | COMPLETE HEART BLOCK   |
| 15 | PAUSE GREATER THAN 3.0 SECONDS (LONGEST PAUSE SECONDS)               | PAUSE GREATER THAN 3.0 SECONDS                                       |
| 16 | AVERAGE HEART RATE LESS THAN OR EQUAL TO 40 FOR ANY ONE HOUR         | AVERAGE HEART RATE LESS THAN OR EQUAL TO 40 FOR ANY ONE HOUR         |

|      | Reported Term               | Preferred Term              |
|------|------------------------------------|------------------------------------|
| 17   | MARKED SINUS BRADYCARDIA ( )       | MARKED SINUS BRADYCARDIA           |
| 18   | INTERMITTENT ECTOPIC ATRIAL RHYTHM | INTERMITTENT ECTOPIC ATRIAL RHYTHM |
| 19   | INTERMITTENT JUNCTIONAL RHYTHM     | INTERMITTENT JUNCTIONAL RHYTHM     |
| 20*  | OTHER: <FREE TEXT>                 | OTHER                              |
| 21*  | NO DATA OBTAINED                   | NO DATA OBTAINED                   |
| 99*  | COMMENTS: <FREE TEXT>              | COMMENTS                           |
| 100* | GOOD QUALITY                       | GOOD QUALITY                       |
| 101* | ARTIFACT                           | ARTIFACT                           |
| 102* | SIGNIFICANT ARTIFACT- THROUGHOUT   | SIGNIFICANT ARTIFACT- THROUGHOUT   |
| 103* | BASELINE WANDER                    | BASELINE WANDER                    |
| 104* | MISSING LEADS                      | MISSING LEADS                      |
| 105* | HIGH OR LOW AMPLITUDE SIGNAL       | HIGH OR LOW AMPLITUDE SIGNAL       |
| 106* | 60 HZ NOISE                        | 60 HZ NOISE                        |

\* Not summarized, only presented in the listings.

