## 6.2 Safety endpoints

Treatment-emergent period is defined as the time from first study treatment intake up to 6 weeks (inclusive) after last study treatment intake.

- Treatment-emergent AEs, SAEs, and AESIs#;
- AEs leading to premature discontinuation of study treatment;
- Changes in 12-lead ECG variables (HR, PR, QRS, QT, QT corrected for heart rate on the basis of Bazett's formula [QTcB] and QT corrected for heart rate on the basis of Fridericia's formula [QTcF]), from pre-dose to selected post-dose assessments (1 h, 2 h, 3 h, 4 h, 5 h, 6 h) on Day 1 and on day of study drug re-initiation;
- Occurrence of treatment-emergent 12-lead ECG outliers (e.g., HR, PR, QTc defined in the Statistical Analysis Plan [SAP]);
- Occurrence of treatment-emergent 12-lead ECG abnormalities;
- Occurrence of treatment-emergent ECG-Holter abnormalities on Day 1;
- Change in SBP and DBP from baseline up to EOS;
- Change in FEV1 and FVC, expressed in absolute value (L) and percent value from baseline up to EOS;
- Occurrence of treatment-emergent decrease of FEV1 or FVC > 15% from baseline values;
- Change in laboratory parameters (hematology, blood chemistry, and urinalysis) from baseline up to EOS;
- Treatment-emergent laboratory abnormalities according to CTCAE 2010 v4.03 [CTCAE 2010] and FDA guidelines [FDA 2009] (for ALT/AST/TBL);
- Change in protein-to-creatinine ratio from baseline to EOT;
- Change in body weight from baseline to EOT.

#AESI considered for the analyses are described in [Appendix 3](#).

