#### *11.4.3.2.3 24-hour Holter ECG*

Treatment-emergent abnormalities as assessed by 24-hour Holter ECG monitoring will be summarized by dose group and presented similarly to AEs. Hourly mean HRs will be summarized descriptively.

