**5.8.7.2 24 hour Holter-ECG**

Holter-ECG monitoring is performed for 24 hours at Visit 1 (Screening) and at Visit 2 (Randomization/ Day 1). The 24 hour Holter-ECG parameter collected is the hourly mean heart rate (bpm).

The hourly records are time-matched between these two visits and the corresponding change for each matched time point is computed.

The following endpoints are defined:

- Occurrence of treatment-emergent Holter-ECG-Holter abnormalities on Day 1;
- Absolute time-matched hourly mean heart rate (bpm) change from Visit 1 (Screening) to Visit 2 (Randomization/ Day 1) at each hourly timepoint up to 24 hours post-dose for;

- Holter-ECG- variables

The following analysis parameter is defined:

- ECG Mean Heart rate (beats/min) .

For this analysis parameter, the following analysis variables are defined (see Section 11 for further details):

- Baseline value at each hourly time point (i.e. hourly measurements at Visit 1)
- Analysis value at each post-baseline assessment (i.e., hourly measurements at Visit 2)
- Absolute time-matched change from Visit 1 (Screening) to Visit 2 (Randomization/ Day 1) at each hourly time point.

- Holter-ECG qualitative findings

For each Holter-ECG, the cardiologist provides his overall interpretation (Normal/ Abnormal) and describes the potential findings in the comment section. Each finding reported for the Holter-ECG performed on Day 1 are considered treatment-emergent.

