#### ***10.9.3.2 24 hour Holter-ECG***

Quantitative descriptive statistics are presented for the hourly mean heart rate (bpm) by time interval for measurements performed on Visit 2 (Randomization/ Day 1).

The hourly records are time-matched between Visit 1 (Screening) and Visit 2 (Randomization/ Day 1) and quantitative descriptive statistics for the corresponding change by time interval are presented.

The evolution of the values over time for the hourly mean heart rate (bpm) on Visit 2 (Randomization/ Day 1) is provided in graphical format (mean and 95% CI for the absolute value for each time interval and treatment group).

The evolution of the change from time-matched screening holter on day 1 for the hourly mean heart rate (bpm) is similarly provided in a graphical format (mean and 95%CI for the time-matched change for each time interval and treatment group)

Treatment-emergent Holter-ECG findings are tabulated by treatment group.

All Holter-ECG data are listed by treatment group, subject and visit. A listing of all Holter-ECG abnormalities is also provided.

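### SAP Table 13 sends free-text OTHER Holter findings to listings only, although the protocol and the SAP's own text say Day 1 Holter findings are tabulated by treatment group

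*SAP*

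**What the plan says.** Protocol 6.2 lists as a safety endpoint "Occurrence of treatment-emergent ECG-Holter abnormalities on Day 1". It does not limit the endpoint to a set of named findings. Protocol 11.4.3.2.3 gives the analysis: "Treatment-emergent abnormalities as assessed by 24-hour Holter ECG monitoring will be summarized by dose group and presented similarly to AEs".

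The SAP carries this forward. Section 5.8.7.2 states: "Each finding reported for the Holter-ECG performed on Day 1 are considered treatment-emergent". Section 10.9.3.2 states: "Treatment-emergent Holter-ECG findings are tabulated by treatment group". The same section adds: "A listing of all Holter-ECG abnormalities is also provided".

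SAP 11.2.14 then explains that findings are extracted from the central reader's comment fields, and Table 13 gives the terms. Rows 1 to 19 are named rhythm, conduction and rate findings. Row 20 is "OTHER: <FREE TEXT>", row 21 is no data obtained, row 99 is "COMMENTS: <FREE TEXT>", and rows 100 to 106 describe recording quality (good quality, artifact, noise, missing leads and the like). Rows 20, 21, 99 and 100 to 106 carry an asterisk, whose footnote is "Not summarized, only presented in the listings".

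**The concern.** Most of the starred rows say something about the recording, not the patient, and leaving them out of a summary is sensible. OTHER is different in kind. It sits among the findings to be extracted, and its natural use is for a finding that none of the 19 named terms fits. Grouping it with the technical codes removes a category of abnormality from the table that reports the endpoint.

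The display matters because first-dose effects on heart rate and AV conduction are a named concern of this study (Protocol 3.2 and 5.1.4.2). The Day 1 Holter runs to 24 hours after dosing (Protocol 7.2.3). The hourly 12-lead ECGs stop at discharge, which may be at 6 hours (Protocol 7.2.2). After discharge the Holter is the only scheduled rhythm recording that day. A reader who takes the findings table as the full summary of that recording would be taking a partial one.

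**Working it through.** The documents state no rate, precision or sample size for this endpoint, so there is no figure to reproduce. The check is a comparison of texts, followed by a small illustration.

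**Tracing one case.** Take a subject whose Day 1 Holter has one finding, entered as OTHER, and none from rows 1 to 19.

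1. Protocol 6.2: if the finding is an abnormality, the subject meets the endpoint. No list restricts it.
2. Protocol 11.4.3.2.3: it should be summarized by dose group in the style of adverse events. Protocol 11.4.3.1.1 shows what that style is: subjects with at least one event, then subjects by class and by term.
3. SAP 5.8.7.2: the finding is treatment-emergent, because it is on the Day 1 Holter.
4. SAP 10.9.3.2: as a treatment-emergent finding, it belongs in the table by treatment group.
5. SAP Table 13 footnote: as a row 20 entry, it is kept out of that table.

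Steps 4 and 5 cannot both be followed.

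**Is the exclusion declared?** SAP section 4 records changes and clarifications to the protocol's analyses. Its only Holter entry (4.3.4) adds the time-matched change in hourly mean heart rate. Dropping OTHER is neither mentioned nor justified.

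**Is it consistent with the 12-lead analysis?** SAP 10.9.3.1 summarizes subjects with any treatment-emergent qualitative 12-lead abnormality by category and reported term. It states no exclusion of free text.

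**Does another Holter output catch the case?** SAP 11.2.13 derives the cardiologist's overall reading as NORMAL or ABNORMAL, but 10.9.3.2 plans no table of it. The listings do show the finding.

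**Illustration of size.** Inputs: 12 subjects per active group and 12 + 4 = 16 in pooled placebo (Protocol 3.1, SAP 10 and 10.2), assuming planned sizes and a Day 1 Holter for everyone. The weight of one uncounted subject in an any-abnormality count is 1/n:

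| Group | n | One subject | Shown if omitted (95% CI) | Shown if counted (95% CI) |
|---|---|---|---|---|
| Active dose | 12 | 1/12 = 8.3 points | 0/12 = 0% (0 to 26.5%) | 1/12 = 8.3% (0.2 to 38.5%) |
| Pooled placebo | 16 | 1/16 = 6.3 points | 0/16 = 0% (0 to 20.6%) | 1/16 = 6.3% (0.2 to 30.2%) |

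The intervals are Clopper-Pearson, for scale only; the SAP does not plan them for Holter findings. The rates for the individual terms in rows 1 to 19 do not change, and a subject with both a named finding and an OTHER finding is still counted through the named one.

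**The case against.** The strongest case on the other side is that little of clinical weight can be lost.

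- **Adverse event route.** Protocol 7.2.3 requires clinically relevant Holter abnormalities to be reported as AEs or SAEs. SAP 10.9.1 tabulates these by onset, including Day 1 after dosing, and matching terms also enter the heart rate and rhythm category of special interest. A reader might infer that an OTHER finding appears in no table at all. The documents do not support that. What stands is narrower: the AE route depends on the physician's judgment of relevance, so it does not stand in for the central reader's findings.
- **Coverage of the main risk.** A reader might also infer that the first-dose conduction signal is hidden. It is not. Rows 10 to 17 already tabulate second-degree, high-grade and complete block, pauses over 3 seconds, an hourly average rate of 40 or less, and marked sinus bradycardia. First-degree block has no row, but PR above 200 ms is tabulated from the 12-lead ECGs (SAP Table 7 and 10.9.3.1), though only at those recording times. Hourly mean heart rate from the Holter is summarized whatever Table 13 says.
- **Bias between arms.** It is tempting to say that the rule lowers rates more in the active arms. The documents give no count of OTHER findings and nothing on how they would divide between arms.
- **Meaning of OTHER.** No passage defines it. Reading it as the place for abnormalities outside the named list is the natural inference from its position in Table 13, but it is an inference.
- **Missing shells.** The list of tables in SAP section 13 has no content in the text available, so a planned table of the overall interpretation cannot be ruled out.
- **Display only.** The endpoint definition is intact and all Holter data are listed; with about 64 subjects the entries can be found by reading.

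These points limit the reach of the concern. None reconciles the footnote with SAP 5.8.7.2 and 10.9.3.2 or with Protocol 11.4.3.2.3.

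**Conclusion.** The point holds as an internal conflict in the SAP and an undeclared departure from the protocol's analysis of a safety endpoint. Its effect is confined to the Holter findings table: subjects whose only Day 1 finding is OTHER are left out of it. No data are lost and the endpoint is not redefined.

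The number of such subjects is unknown and may be zero. Each would be worth 8.3 points in an active arm or 6.3 points in pooled placebo in an any-abnormality count, given planned group sizes. The SAP does not explicitly plan such a count, although presentation in the style of adverse events implies one. The conclusion assumes that OTHER holds abnormalities and that no unseen table shell already covers them. It is a descriptive-display correction that should be made because it is nearly free.

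**What to change.** In SAP Table 13, remove the asterisk from row 20. In SAP 10.9.3.2, state that OTHER findings are tabulated by treatment group, either coded to short terms while the study team is still blinded or shown as a single OTHER row. Add a row for the number and percentage of subjects with any treatment-emergent Day 1 Holter abnormality. Keep row 21 and rows 100 to 106 as listing only. If the sponsor prefers to keep OTHER out of the table, SAP section 4 should declare and justify that.

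Two optional additions are a blinded review of row 99 comments for clinical findings, and a table of the overall NORMAL or ABNORMAL reading with the screening reading beside it.

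The cost is a few lines of SAP text, one table shell and, if terms are coded, blinded coding of the free-text entries. No new data are needed.
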